4.1 Inclusion/Exclusion Criteria

Participants will include 170 (90 completers) physically healthy premenopausal females reporting past-month suicidal ideation (but acceptably low imminent suicide risk for outpatient care) receiving treatment as usual at an outpatient mental health clinic in Chicago, **and** 60 (40 completers) physically healthy premenopausal females with no lifetime history of SI and no DSM-5 diagnoses in the past five years (total 230 participants). The HC group inclusion and exclusion criteria are identical *except* where indicated below. Although the HC group will not undergo exogenous hormone stabilization, they will be required to meet identical medical criteria in order to best match the experimental group.

Of note, we will not exclude those without smartphones, and a smartphone will be provided to a subject if they do not have one.

To participate, individuals must meet all of the following inclusion/exclusion criteria:

- (1) Must be biologically **female assigned at birth** and between the ages of **18-45 years**.

Justification: Females younger than 18 or older than 45 may have inconsistent menstrual cycles or may be postmenopausal and therefore no longer cycling.

- (2) Must self-report **normal menstrual cycles** between 21 and 35 days.

Justification: Abnormal menstrual cycle lengths or variability in lengths could introduce error variance into the experiment and could reduce confidence regarding the timing of the experimental manipulation to cycle events.

- (3) Must be under the **current care** of an outpatient mental health provider with whom they are comfortable discussing history of suicidal ideation and are able to visit at least once every 3 months, or they must be willing to begin visiting an outpatient mental health provider at least once every 3 months.

Justification: Because we intend to recruit females with current suicidality, engagement with a mental health provider is required as a protective measure to ensure that participants have access to treatment if needed.

HC group: criterion 3 not applicable; HC participants should *not* be under the care of an outpatient mental health provider for diagnosis or treatment of a psychiatric condition.

(4) If the person has children, they must be at least **1 year postpartum**.

Justification: The postpartum period can be characterized by altered hormone levels and changes; therefore, postpartum females may introduce error variance into the experiment.

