Using Metricwire App		X	X	X		X			

Table 1b. substudy activities and timeline.

The proposed substudy characterizes 1) normative cycle-related variation in neuroactive steroids and mRNA expression, and 2) group-related differences (i.e., past-month SI vs HC) in trajectories of GABAAR subunit change across the cycle. 60 healthy controls (HC) with no SI will be recruited to gain a completer number of 40 for a two-month long observational substudy, in which five lab visits across one menstrual cycle (timed identically to mirror the observations across one medication phase of the experimental trial) will capture baseline molecular/genetic changes for between-group comparisons. The basic timeline for participation can be seen in table 1b.

The **double-blind crossover experimental design** is identical to that used during the PI's recently-completed trial (K99MH109667; Fig. 6). The TOP (red) panel shows natural perimenstrual hormone withdrawal in the placebo condition; the BOTTOM (black) panel shows prevention of hormone withdrawal in the active E2+P4 stabilization condition. THIS IS NOT A CLINICAL EFFICACY TRIAL, but a RCT design will probe the effect of hormone withdrawal (vs. stabilization) on proximal suicide risk and mediators. Participants will be randomized to condition order A (see Table 1 above; Active E2+P4, washout cycle, then Placebo) or condition order B (Placebo, washout cycle, then Active E2+P4). Investigational Drug Services will manage the double-blind. In each two-week condition, participants will wear a weekly patch (E2 or placebo) and take a daily pill (P4 or placebo). Because this manipulation simply delays natural E2+P4 changes⁹⁶, and given our previous finding of benefit¹², this manipulation is *not expected to pose greater risk than a normal menstrual cycle*.

Timing and Duration. Participants will receive the first seven-day transdermal E2 patch (or placebo patch) and begin daily oral P4 (or oral placebo) at a lab visit scheduled seven days after a positive urine ovulation test (+7 in Fig 6). This coincides with a time in the natural cycle when E2+P4 are already elevated. The weekly patch will be changed at the lab visit on day +14. The goal of this E2+P4 manipulation is to extend and maintain the mid-luteal phase hormone profile beyond the point in the cycle (i.e., around day +10) that would normally be associated with natural hormone withdrawal. Therefore, the active condition effectively prevents perimenstrual E2 and P4 withdrawal.

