Formulation and Dose. Estradiol. Peak E2 with transdermal E2 patches (~45 pg/mL) correspond roughly to normative luteal E2 levels⁹⁶. These E2 levels are expected to maintain stable mRNA expression of 3 α -HSDII during the experimental period, stabilizing biosynthesis of neuroactive steroids. Transdermal E2 demonstrates reduced thromboembolic risks relative to oral E2. **Progesterone.** Although transdermal synthetic progestins exist, these molecules have confounding effects at androgen and mineralocorticoid receptors. Thus, oral micronized progesterone 200mg/day will maintain luteal ranges (~13 ng/dL)⁹⁶ as in the prior trial¹²; this dose of P4 is expected to buffer neuroactive steroid change by increasing precursors. **Standardized times for evening dosing (7 pm) and lab visits (7-11am)** will minimize variability in neuroactive steroid levels due to timing. Typical within-participant variation in emotional symptoms, physical premenstrual symptoms, and cycle length will maintain participant blind. Demand characteristics will be minimized by telling participants that responses to hormones differ, and they may experience positive or negative moods. Blinding was excellent in our completed trial, with medication-day condition guesses only slightly more accurate than chance (53% accurate). **Manipulation Checks.** In the prior trial, we found that the hormone stabilization condition (E2+P4) was associated with elevated (maintained) levels of E2 and P4 on day +14 (see Figure 6) relative to a drop in E2 and P4 observed in the placebo condition. We will once again measure E2 and P4 in this trial to confirm stabilization.

[figure not shown]

Fig. 6. Experimental Conditions

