During the study, each participant will also wear an *Oura Ring*, a wearable ring device (that includes a pulse plethysmograph (PPG) and temperature sensors) throughout the study; these rings, which have been validated to index heart rate and heart rate variability (measures of physiological arousal), as well as changes in basal body temperature, will serve the dual purpose of measuring both physiological arousal and progesterone-related temperature changes across the cycle.

NOTE: A prior version of the protocols utilized lab-based measures of physiological arousal using a traditional EKG. However, given ongoing concerns regarding close contact during the COVID-19 pandemic, the NIMH program officer for the grant funding the present study has approved a change from lab-based cardiovascular physiological recording using EKG to ambulatory assessment of physiological arousal using the Oura Ring.

Repeated Laboratory Visits for HC participants (Aim 3 substudy)

HC participants will complete 5 60-minute lab visits across one menstrual cycle. Repeated lab visits will be timed identically in the HC substudy group as in the primary group (i.e., 5 lab visits scheduled on days +7, +10, +14, +18, and +22 relative to a positive urine ovulation test. Participants will undergo a blood draw, urine pregnancy and standard drug screen (day +7), and report health behaviors and illness. Participants will **not receive any experimental patch application**, will not complete cognitive tasks, and will not complete interviews.

Debriefing Visit (1 hour)

After completing both randomized conditions, participants will be asked to attend for a 1 hour debriefing session with [name] either in-person or virtually in which participants will be unblinded, learn more about the purpose of the study, have any concerns or questions participants may have about the study answered and addressed, and evaluate the participant's current risk of suicide upon study completion.

Debriefing Visit for HC participants (Aim 3substudy)

HC participants will not be asked to attend a debriefing session, as they do not complete randomized double-blind experimental conditions, and they do not have suicide risk to assess.

CLINICAL LABORATORY ASSESSMENTS AND SAMPLING:

A point-of-care urine pregnancy test will be completed in our laboratory on site at the first visit of both conditions. A positive pregnancy test will result in termination of participation and will be managed by [name].

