Self-Reports. Self-report **surveys** from the enrollment visit will be repeated at each laboratory visit, with instructions to report symptoms in the past week or since the last visit. The "since last visit" version of the C-SSRS¹⁰⁴ **interview** will be used to precisely measure discrete self-injurious thoughts and behaviors at each laboratory visit; responses will be coded into suicide outcomes using the C-CASA⁹⁸.

We will operationalize behavioral hyperarousal (reactivity) as a longer response time when matching emotional faces relative to shapes. We will utilize these measures as independent predictors of proximal suicide risk, as well as variables with which to further validate *BiAffect* indices (below).

Physiological Arousal. Following the laboratory visit, participants will be mailed an Oura Ring in the appropriate size, along with instructions for charging and use, and asked to wear the ring as much as possible while in the study. This commercially available product is intended for fitness tracking and recreational use. It is worn on the middle finger and also uses PPG technology along with mechanical sensors to measure physical activity, sedentary behaviors, sleep, heart rate, oxygen saturation, and body temperature.

Participants will also be asked to use the Oura app- this commercially available application is required to collect data from supported Oura products. It is publically and free available for both Android and iOS devices in their respective app stores. Data from the Oura Ring will be transferred to the Oura smartphone app, and later to the Oura cloud storage service (where it can be retrieved later by the study team) using an Oura Ring app account created by the study team using the participant's confidential study email address (e.g., [contact]). Data collected and uploaded to the cloud will not include IP address or any other participant-identifying information.

Self-reports and physiological arousal for HC participants (Aim 3 substudy).

HC participants will not be asked to complete self-report surveys or cognitive tasks at laboratory visits. They will not wear an Oura Ring or use the Oura app.

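### The ring's second stated purpose is to track progesterone-related temperature and its data pass through an app participants use, but the plan does not protect the blind against that possible cue

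*Protocol*

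**What the plan says.** All Protocol references are to Section 6.0 unless stated.

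- **Why the ring is used.** A note under Repeated Laboratory Visits says the ring replaced lab-based EKG because of COVID-19 contact concerns. Arousal is therefore its first purpose. The same text says these rings "will serve the dual purpose of measuring both physiological arousal and progesterone-related temperature changes across the cycle".
- **Who handles the data.** Of the ring, the Physiological Arousal paragraph says "This commercially available product is intended for fitness tracking and recreational use". It adds: "Participants will also be asked to use the Oura app- this commercially available application is required to collect data from supported Oura products". On the data route it says: "Data from the Oura Ring will be transferred to the Oura smartphone app, and later to the Oura cloud storage service". The study team retrieves the data afterwards, "using an Oura Ring app account created by the study team".
- **Which phone.** Section 4.1 does not exclude people without smartphones: "a smartphone will be provided to a subject if they do not have one".
- **When it is worn.** Throughout the study, so through the baseline cycle, both condition cycles and the washout cycle (Table 1a).
- **How the blind is kept.** "Investigational Drug Services will manage the double-blind". The Formulation and Dose paragraph relies on ordinary within-person variation in symptoms and cycle length. It also tells participants that responses to hormones vary and that mood may go either way. Its supporting evidence comes from the prior trial: "Blinding was excellent in our completed trial, with medication-day condition guesses only slightly more accurate than chance (53% accurate".
- **What is rated.** The SAP's Outcome Specification takes ideation from a daily self-report score, hopelessness and agitation from daily self-report items, and planning and attempts from a daily phone screen.

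**The concern.** The plan puts a device intended to follow a progesterone-related signal on participants who are meant not to know whether they are receiving progesterone. They also hold the app through which its data flow. If the signal is visible and readable, some participants could work out their condition during the days that carry the primary contrast.

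Expectancy would then act on the ideation rating. It would act on the same days on hopelessness and agitation, which are candidate mediators. The SAP tests mediation only after three results: an effect of the experiment on the suicide outcome, an effect on the mediator, and an association between the two. A shared expectancy shift could contribute to all three, so it bears on the mechanistic question as well as on the treatment contrast.

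Participants are unblinded at debriefing. A condition guess not taken before then cannot be recovered.

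**Working it through.** **1. The chain, link by link**

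| Link | Source | Status |
|---|---|---|
| The ring measures body temperature and is meant to follow progesterone-related change | Protocol 6.0, Repeated Laboratory Visits; Physiological Arousal | Stated |
| Progesterone was maintained on active and fell on placebo at day +14 in the prior trial | Protocol 6.0, Formulation and Dose | Stated |
| Day +14 lies inside the +11 to +17 perimenstrual phase of the primary daily contrast | Protocol 10.0; SAP Analytic Steps | Stated |
| Participants are asked to use the app that receives the data | Protocol 6.0, Physiological Arousal | Stated |
| Unmedicated cycles are available to the wearer for comparison | Protocol Table 1a | Stated |
| The app shows temperature to the wearer | None | Assumed |
| The difference between conditions is large enough to read, and the wearer knows what it means | None | Assumed |

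**2. Safeguards set against the device**

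- Natural variation in symptoms and cycle length makes felt cues unreliable. It does not deal with a recorded temperature signal.
- Neutral expectancy instructions may reduce the effect of a correct inference. They do not prevent the inference.
- The study-created account and email address protect identity (Protocol 7.0, Confidentiality), not the blind.
- No passage masks the display, restricts viewing, limits staff access to ring temperature on blinding grounds, or names the ring as a risk to the blind.

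**3. The plan's one blinding figure**

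The 53% cannot be reproduced because no counts are given. The prior crossover trial had 30 participants, so two sets of counts are tried as assumptions, with exact binomial 95% intervals:

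- one guess each: 16/30 = 53.3%, interval 34% to 72%;
- one guess per condition: 32/60 = 53.3%, interval 40% to 66% (treating guesses as independent).

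On either count the figure does not exclude moderate unblinding. No passage describes a ring in that trial, so nothing shows that the figure covers one.

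**4. How sensitive the primary test would be to a reporting bias**

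This is an illustration on the SAP's own yardstick, not an estimate.

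- SAP inputs for ideation: 85 completers, 24 daily observations each, ICC .64, 3 predictors, one-tailed alpha .004, f² = .10.
- Effective N = 85 × 24 / (1 + 23 × .64) = 2040 / 15.72 = 129.8 (SAP: 130).
- Power from the noncentral t with df = 130 − 4 = 126, critical t = 2.695 and noncentrality √(.10 × 130) = 3.61: .817 (SAP: .81). The SAP row is reproduced.
- Smallest observed f² that reaches significance: 2.695² / 130 = .056.
- With no true effect and a bias in the hypothesised direction of assumed size f², noncentrality is √(f² × 130):

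| Assumed bias (f²) | 0 | .005 | .01 | .02 | .03 | .05 |
|---|---|---|---|---|---|---|
| False-positive rate | 0.4% | 3% | 6% | 14% | 24% | 45% |

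The documents do not indicate which column applies, if any beyond the first.

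**The case against.** The strongest reply is that the decisive step is not in the documents. They do not say what the app displays, or how large or readable a temperature difference the study progesterone would produce. That stands, and it rules out the stronger reading a reader might take: that the ring reveals the condition, or that the blind fails. The documents support only a possible cue.

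A reader might also infer that the ring was picked to expose progesterone. The protocol says otherwise: it came in as the substitute for EKG, and temperature is its second purpose.

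The expectancy instructions deserve credit. Harm needs a correct inference and also a consistent shift in ratings, and those instructions are aimed at the second. They reduce the concern without removing it.

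A reader might conclude that no condition guess will be taken. The text does not go that far. The prior trial collected guesses, and the protocol describes the present crossover design as the same as that trial's, so the check may carry over. It is simply not written down.

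The reach is limited too. Seven of the twelve SAP outcomes are not symptom reports: accelerometer activity, typing instability, two autonomic measures, allopregnanolone and two gene-expression measures. The remaining five rest on participants' own ratings or answers, and they include all three primary suicide outcomes.

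**Conclusion.** The concern holds as a gap in the protection of the blind. As written, the plan leaves a possible read-out of the manipulated hormone with the people who rate the main outcomes. Its safeguards were not framed for this device, and its one piece of blinding evidence comes from a trial in which no ring is described.

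The conclusion that there is a cue rests on two assumptions: that the app shows temperature to the wearer, and that the difference can be read and interpreted. Any bias would also need a directional effect on ratings. Its size would depend on the share of participants who infer the condition and on how far expectancy moves their ratings. The documents give neither, so no magnitude is claimed. The false-positive table shows only that the SAP's test would be sensitive to modest bias if one existed.

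The change should be made because it is cheap and because a guess not collected before debriefing is lost.

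**What to change.** 1. Where the app allows, hide temperature and cycle-related displays on the study-created accounts until debriefing. Where it does not, instruct participants not to view them during the two conditions. The protocol should state which applies. The app is needed for data collection, so confirm first that hiding displays loses no data.
2. Keep ring temperature data from staff who run the daily calls and laboratory visits until the participant has completed both conditions. The protocol says only that the team retrieves the data later, not who sees them or when.
3. Expressly schedule a condition guess at the end of each condition, before debriefing, and report its accuracy alongside the primary contrast. Accuracy above chance would need careful reading, since it could come from felt benefit as well as from the ring.

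The cost is one account setting or instruction, a data-access rule and two survey items. Participants lose some app feedback during the study. No dose, visit or clinical rule changes.
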